treatments such as radiotherapy and chemotherapy at many cancer centres across the world, its use has not been established in NHS settings. The main difficulties in introducing its use into routine clinical practise is the lack of expertise in its use as well as the lack of availability of clinically approved hyperthermia machines at any UK cancer centre. Guys Cancer Centre is the first centre nationally to introduce a CE marked hyperthermia machine (hydrosun®-TWH1500) for patient use in the NHS.

Patients presented with inoperable/recurrent disease usually have limited prognosis and any associated symptoms such as pain, discharge, infection, and bleeding significantly affect their quality of life. Several publications support the clinical use of hyperthermia with palliative radiotherapy in multiple tumour types (19). Datta et.al provides a summary of the clinical outcomes of 38 clinical trials across various tumour sites including breast, head and neck and skin melanoma comparing radiotherapy (1717 patients) versus thermoradiotherapy (1761 patients) and reported an overall clinical response of 54.9% in thermoradiotherapy groups vs 38.9% in the radiotherapy alone group (odds ratio: 2.3, 95% confidence interval 1.95–2.72, $p < 0.001$) (19). In a randomised phase 3 trial of patients with superficial measurable tumours treated with either radiotherapy alone or radiotherapy followed immediately by hyperthermia (42.5 degrees C, 45-60 min), a better CR rate was observed with a combination of radiotherapy and heat (62 and 67%) compared with irradiation alone (40 and 0%) in tumours less than 3 cm in diameter in the breast, trunk, and extremities despite no difference in overall CR between the two arms (20).

In head and neck cancer, a systematic review and meta-analysis comparing the efficacy of hyperthermia plus radiotherapy over radiotherapy alone showed an overall CR of 62.5% in the combination treatment versus 39.6% in the radiotherapy alone group (21). Moreover, a systematic review investigating the role of hyperthermia in the treatment of local recurrent breast cancer (LRBC) showed that the combination of hyperthermia with radiotherapy achieved a complete response rate of 60.2% compared to 38.1% for radiotherapy alone (22). However, most of the previous evidence is based on older hyperthermia and radiotherapy techniques, which have been disregarded by many oncologists as non-comparable to current standard of care.

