	5. To assess patient-reported outcomes measures (PROMs)	
5. PROMs assessment using the European Organization for Research and Treatment of Cancer (EORTC) Quality of Life Core Questionnaire (QLQ-C30), European Organisation for Research and Treatment of Cancer Quality of Life Questionnaire Head and Neck Module (QLQ-H&N43) (for HNSCC cohort)
 
PROMs will be collected at baseline, during treatment (after the 3rd fraction of radiotherapy), 6 weeks post-treatment, 12-weeks post-treatment.

	6. To assess the differences in the efficacy between the lesion(s) treated with radiotherapy with hyperthermia with the lesion(s) treated with radiotherapy alone in those patients with at least 1 additional lesion that is not suitable for treatment with hyperthermia	6. Percentage of best ORR, duration of response and disease control rates at 6 and 12 months in the lesion(s) treated with hyperthermia and radiotherapy versus lesion(s) treated with radiotherapy alone.
	7. To compare clinical outcome of patients treated with superficial hyperthermia in addition to SOC radiotherapy with historical control	7. Retrospectively collect data for historical cohort of similar cancer patients treated with SOC radiotherapy alone

⁵Descriptive primary endpoint: evaluation of the real-world implementation by the NASSS-CAT

Introduction of the new technology into the NHS can be very complex and the process of which cannot be easily captured by the traditional clinical trial endpoints. To this end, the non-adoption, abandonment, scale-up, spread, and sustainability (NASSS) framework allows the description of the complexity in real-world implementation of new technology consisting of six domains including (a) the condition or illness, (b) the technology, (c) the value proposition, (d) the adopter system, (e) the health care organization(s), and (f) the wider system (especially regulatory, legal, and policy issues). The seventh domain is cross-cutting, considering how all these domains interact and emerge over time (27). Extending the NASSS framework and building on a complexity assessment tool (CAT), four NASSS-

CAT tools were previously developed to apply the complexity principles to evaluate the introduction of technology in healthcare setting (28). These includes NASSS-CAT SHORT, NASSS-CAT LONG, NASSS-CAT PROJECT and NASSS-CAT INTERVIEW (see appendix). We will use these tools to evaluate the descriptive part of the primary endpoint of this study.

7. Study design & Flowchart

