○ Study design

This is a prospective study to assess the real-world implementation of superficial hyperthermia (wIRA) in combination with SOC palliative radiotherapy in cancer patients not suitable for radical treatment and have superficial lesion(s) suitable for wIRA treatment. All eligible patients will be recruited in the study by the clinical team following discussion with the chief investigator or the designated clinical sub-investigator. Patients will be consented for palliative radiotherapy as per standard treatment. The radiotherapy dose delivered will be clinician's choice based on SOC table 1 schedules.

Table 2: Schedule of radiotherapy and hyperthermia

Palliative radiotherapy (Primary vs Re-irradiation)	Dose	Fractions	Radiotherapy	Hyperthermia
Primary or Re-irradiation (previous standard palliative dose)*^	27Gy	6	Twice per week	Once per week
Re-irradiation (previous radical dose)*^	20Gy	5	Once a week (up to 5 weeks)	Once per week
Primary or Re-irradiation (previous standard palliative dose)*^	20Gy	5	Daily over 1 week	Twice per week
Re-irradiation (previous radical or palliative dose)*^	20Gy	10	Daily over two weeks	Twice per week
Primary or Re-irradiation (previous standard palliative dose)*^	36Gy	6	Once a week	Once per week

*The combined dose from previous RT and proposed RT fractionation will not exceed tolerance dose for critical organs (assuming recovery if necessary, as per routine clinical practice). If completing the full radiotherapy schedule would result in exceeding the tolerance dose to critical organs, treatment may be administered on a weekly basis until the tolerance threshold is reached.

[^]The combined dose from previous RT and proposed RT fractionation will not exceed tolerance dose for critical organs (assuming recovery if necessary, as per routine clinical practice) and the combined dose to soft tissue of the irradiated area will not exceed 70Gy in equivalent 2Gy per fraction (without assuming recovery).

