1. Patient with histologically confirmed incurable or recurrent cancers with disease [at least one superficial lesion(s) or lymph node(s)] suitable for hydrosun® TWH1500 treatment
2. Patient suitable for SOC palliative radiotherapy or re-irradiation with one of the pre-specified palliative radiotherapy dose and fractionation (Table 1 above)
3. Aged ≥18 years old
4. Eastern Cooperative Oncology Group (ECOG) performance status 0 to 2
5. Capacity to consent

- **Subject exclusion criteria**

1. No superficial tumour lesion or lymph node that is suitable for hydrosun® TWH1500 treatment
2. Patients are not suitable for one of the pre-specified palliative radiotherapy dose and fractionation (table 1 above)
3. Has known psychiatric or substance abuse disorders that would interfere with cooperation with the requirements of the study

- **Collection of biological samples for translational research**

We propose to develop a detailed investigation of total immune profile of patients following palliative radiotherapy +/- superficial hyperthermia to tumour lesion(s). Some of these patients may subsequently undergo palliative anti-PD1 or anti-PDL1 checkpoint antibody as part of the standard treatments. Understanding the immune responses to various treatments will help us to stratify and optimize patients' treatments and to combine different treatment modalities in a personalized manner. We also aim to uncover prognostic and predictive biomarker that could help to deliver a more personalized treatment in cancer patients undergoing palliative radiotherapy with superficial hyperthermia who may or may not subsequent anti-PD1 antibody as part of the standard of care.

We will assess peripheral immune responses as well as free and vesicular Hsp70 in the bloods from patients undergoing treatment at baseline and post-treatments:

- 1) palliative radiotherapy (RT) + hyperthermia: baseline, pre-hyperthermia treatment, post-hyperthermia/radiotherapy treatment (post-third or fourth fraction of RT), 6 weeks (+/- 2 weeks) post hyperthermia/radiotherapy, 12 weeks (+/- 2 weeks) post hyperthermia/radiotherapy and at the first disease progression post hyperthermia/radiotherapy.

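### Secondary objective 6 compares heated lesions with lesions that cannot be heated, so a difference between them cannot be read as an effect of hyperthermia

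*Protocol*

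**What the plan says.** Objective 6 appears in the Synopsis (Section 4), in the list of secondary objectives in Section 6, and in Table 1. In each place it is about differences in efficacy, and it is confined to patients with "at least 1 additional lesion that is not suitable for treatment with hyperthermia". The matching endpoint contrasts best objective response rate, duration of response and disease control at 6 and 12 months "in the lesion(s) treated with hyperthermia and radiotherapy versus lesion(s) treated with radiotherapy alone".

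Eligibility fixes which lesions are heated. Section 7 (Study design) describes patients who "have superficial lesion(s) suitable for wIRA treatment". Section 8 excludes a patient with "No superficial tumour lesion or lymph node that is suitable for hydrosun® TWH1500 treatment". No size or site limit is given for suitability.

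On radiotherapy, Section 7 states: "The radiotherapy dose delivered will be clinician's choice based on SOC table". The schedules in Table 2 run from 20 Gy in 5 or 10 fractions to 36 Gy in 6, and the available rows depend on earlier irradiation.

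Table 1 defines best objective response rate as a proportion of patients, judged on the sum of diameters of the target lesions.

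**The concern.** The objective is worded as a comparison of efficacy, and it is the only concurrent comparison in the study, since objective 7 uses historical controls. Yet the unheated lesion is in the comparison because it could not be heated. Whatever makes a lesion unsuitable may also affect how it responds to radiotherapy, and no caveat against a causal reading is written.

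What is at stake is interpretation. A reader could take the difference as evidence for or against hyperthermia when it supports neither. Section 14 says that data from this study will be used to size an extension or a future interventional study. It does not say which outcomes will be used, but a contrast of this kind would be a poor basis.

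**Working it through.** The Protocol gives no effect size, power or sample size for objective 6, so there is no figure to reproduce. The check is on structure.

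**1. Which combinations of lesion and treatment occur** (from Sections 6, 7 and 8)

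| Lesion | Radiotherapy + heat | Radiotherapy alone |
|---|---|---|
| Suitable for the device | yes | none described |
| Not suitable | none | yes |

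The two off-diagonal cells are empty. There is no randomisation of lesions and no provision for leaving a suitable lesion unheated. Suitability and treatment are the same variable.

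**2. What the contrast estimates**

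Let *a* be the response proportion of suitable lesions with heat, *b* that of suitable lesions with radiotherapy alone, and *c* that of unsuitable lesions with radiotherapy alone. The endpoint gives

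*a* − *c* = (*a* − *b*) + (*b* − *c*).

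The first term is the heat effect. The second is the gap between suitable and unsuitable lesions without heat. Because *b* is never observed, the two terms cannot be separated by any later analysis of these lesions.

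**3. What the document says about the gap**

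The Introduction cites an "overall clinical response of 54.9% in thermoradiotherapy groups vs 38.9% in the radiotherapy alone group", which is 54.9 − 38.9 = 16.0 points, but says nothing about unsuitable lesions. It also cites a randomised trial in superficial measurable tumours with complete response better under heat "compared with irradiation alone (40 and 0%) in tumours less than 3 cm in diameter in the breast, trunk, and extremities". That result shows where heat helped. It gives no radiotherapy-alone rate for deeper lesions or for larger ones. Neither the sign nor the size of *b* − *c* follows.

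Purely to show how the identity behaves, take gaps assumed from −20 to +20 points. They are not estimates.

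| Heat effect (*a* − *b*) | Gap −20 | Gap 0 | Gap +20 |
|---|---|---|---|
| 0 | −20 | 0 | +20 |
| 16 | −4 | 16 | +36 |

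The same design could hide a real effect or display one that does not exist.

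**4. Radiotherapy dose**

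Two sites in one patient can have different irradiation histories, and Table 2 ties its rows to that history. A footnote to Table 2 also lets delivery depend on when critical-organ tolerance is reached, which varies by site. Since no common schedule is required, *b* − *c* may include a dose difference as well as depth and site.

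**5. Unit of response**

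Endpoint 6 is about lesions, but best objective response is defined per patient. Take two target lesions of equal baseline diameter, the unheated one unchanged. The sum then falls by half of the heated lesion's shrinkage, so a 60% shrinkage there gives 60/2 = 30%, a partial response for the patient. The definition returns one result for two lesions that behaved differently. Duration of response, which ends at progression or metastasis, is likewise not specific to a lesion.

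**The case against.** The strongest reply is that this is the sixth secondary objective of an implementation study. Section 14 states that no formal power calculation was done, no test or success threshold is attached, and the criteria for continuing (Section 9, End of Study Definition) are recruitment, implementability and funding. The Protocol nowhere says that a difference will be attributed to hyperthermia. All of this stands, and it keeps the severity low. It does not remove the problem, because the objective is still worded as a difference in efficacy and carries no caveat.

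A second reply is that both lesion types come from the same patients, which controls factors such as performance status and systemic treatment. That is correct. It also means the Protocol cannot be faulted for ignoring the pairing: no unpaired analysis is specified, and the paired method belongs in a statistical analysis plan. Lesion-level differences remain.

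A third reply is that a statistical analysis plan could adjust for them. It could adjust for diameter or site, but not for suitability itself, where the two groups do not overlap.

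Two stronger readings are tempting. A reader might infer that unheated lesions are larger and that the background shows size drives prognosis. The benefit "in tumours less than 3 cm in diameter in the breast, trunk, and extremities" concerns the effect of heat, and the Introduction describes the device as able to heat large areas. A reader might also infer a false gain of known size by setting the 40% complete response quoted for radiotherapy alone against an assumed lower rate. That ignores the 0% quoted beside it and would compare complete response with overall response.

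**Conclusion.** The point holds as a limit on interpretation. Objective 6 cannot isolate an effect of hyperthermia, because suitability fully determines treatment under every route the Protocol describes and because a common radiotherapy schedule is not required. Depth follows directly from the text; site and dose are possible further contributors. The bias has no known direction and no size derivable from the document. A claim that the trial would overstate the benefit of heat therefore goes beyond the evidence.

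The conclusion assumes that the radiotherapy-alone lesions are the unsuitable ones, which is the only reading the eligibility and objective texts support. Severity is low. The per-patient response definition is a separate, smaller defect that leaves the lesion-level endpoint not fully defined.

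**What to change.** - Reword objective 6 in the Synopsis, Section 6 and Table 1 as: *to describe response in heated and unheated lesions of the same patient*. Add that a difference will not be attributed to hyperthermia.
- Restrict the contrast to within-patient pairs of measurable lesions that received the same radiotherapy schedule. This removes the schedule difference but not depth, so the descriptive label is still needed.
- Define response, its duration and disease control per lesion for this endpoint.
- Record depth, site, baseline diameter and delivered dose for each lesion. Section 13 already collects tumour characteristics and treatment details, but does not say they are held per lesion.

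A diameter covariate or a split at 3 cm is not recommended as a remedy, since neither removes the confounding by suitability.

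The cost is wording, a few case report form fields, fewer pairs and a weaker claim. The number of patients with a second, unsuitable lesion is not stated, so the loss of pairs cannot be quantified. No treatment changes.

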Primary	To assess the real-world implementation of superficial hyperthermia using CE marked water-filtered infrared A (wIRA) in addition to palliative SOC radiotherapy	
 1. Quantitative: the total number and types of cancer patients successfully treated with the combination of superficial hyperthermia and palliative radiotherapy. 2. Descriptive: to evaluate the real-world implementation by the NASSS (non-adoption, abandonment, scale-up, spread, and sustainability) framework using NASSS-CAT (complexity assessment tool)
Secondary	1. To assess the best objective response rate (ORR) of the lesion(s) treated with combination of superficial hyperthermia with palliative radiotherapy	
 1. Best ORR: Defined as the proportion of patients achieving either a Complete Response (CR) or a Partial Response (PR). Complete Response (CR): Disappearance of all target lesions.

		Partial Response (PR): $\geq 30\%$ decrease in the sum of diameters of target lesions, taking as reference the baseline sum diameters.
	2. To determine the tolerability and safety profile of superficial hyperthermia in patients receiving SOC palliative radiotherapy	2. Local serious adverse events (SAEs) will be assessed by Common Terminology Criteria for Adverse Events (CTCAE) version 5.0.
	3. To evaluate the median local and global progression-free survival (PFS) and median overall survival (OS) of patients at 12 months after the last patient is recruited	
3. Patients not experiencing an event (progression or death) will be censored at the time of the final analysis at the date last known to be alive and progression-free.
 
Local: refer to the lesions treated by radiotherapy +/- superficial hyperthermia.
 
Global: local and distant (non-treated lesions)
 
PFS: Defined as the time from baseline to the first documented progressive disease (PD) or death from any cause, whichever occurs first.
 
Progressive disease (PD): At least a 20% increase in the sum of diameters of target lesions or development of new lesions, with the date of progression recorded by a clinician in the patient's hospital records.
 
OS: The time from the start of treatment to death from any cause.

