Secondary	
1. To assess the best objective response rate (ORR) of the lesion(s) treated with (1) combination of superficial hyperthermia with palliative radiotherapy; (2) radiotherapy alone
 
2. To determine the tolerability and safety profile of superficial hyperthermia in patients receiving SOC palliative radiotherapy
 
3. To evaluate the median local and global progression-free survival (PFS) and median overall survival (OS) of patients at 12 months after the last patient is recruited
 
Local: refer to the lesions treated by radiotherapy +/- superficial hyperthermia.
 
Global: local and distant (non-treated lesions)
 
4. To assess the median duration of objective response and locoregional control rates of the treated lesion(s) at 6 and 12 months
	
1. Best ORR: Defined as the proportion of patients achieving either a Complete Response (CR) or a Partial Response (PR).
 
Complete Response (CR): Disappearance of all target lesions.
 
Partial Response (PR): ≥ 30% decrease in the sum of diameters of target lesions, taking as reference the baseline sum diameters.
 
2. Local adverse events (AEs) and adverse reactions (ARs) will be assessed by Common Terminology Criteria for Adverse Events (CTCAE) version 5.0.
 
3. PFS: Defined as the time from baseline to the first documented progressive disease (PD) or death from any cause, whichever occurs first.
 
PD: At least a 20% increase in the sum of diameters of target lesions or development of new lesions, with the date of progression recorded by a clinician in the patient's hospital records.
 
OS: The time from the start of treatment to death from any cause.
 
Patients not experiencing an event (progression or death) will be censored at the time of the final analysis at the date last known to be alive and progression-free.
 
4. Duration of Objective Response: Defined as the time from the first documented Complete Response (CR) or Partial Response (PR) to disease progression or metastasis.

		Locoregional Control Rate: The proportion of patients whose primary tumour site remains free from progression.

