The patients will receive hyperthermia either once a week or twice a week (as listed in Table 1) using hydrosun® TWH1500 with palliative radiotherapy. The patients will receive hyperthermia treatment for 1 hour before going for palliative radiotherapy as per standard of care. For patients who will undergo 27Gy/6#, they will receive hyperthermia once a week for three weeks during the course of palliative radiotherapy. For patients undergoing 20Gy/5# over five weeks or 36Gy/6# over six weeks, they will receive hyperthermia once a week. For patients undergoing 20Gy/5# over one week or 20Gy/10# over two weeks, they will receive hyperthermia two times per week during their treatment.

Most of the HNSCC patients will be suitable for palliative pembrolizumab (if the tumours are CPS \geq 1) and the cSCC patients will be suitable for cemiplimab if they have an ECOG performance status \leq 1. We would aim to start palliative pembrolizumab within 6 weeks (+/- 2 weeks) of completing palliative radiotherapy if patients are deemed to be suitable and fit for this treatment as part of the standard of care. LRBC patients will undergo systemic treatments as per standard of care according to their previous treatment histories and breast cancer subtypes.

Patients will be assessed during their treatment for toxicities, and rate of adverse events will be assessed by CTCAE version 5.0. Follow-ups and assessment of response will be done as per standard of care.

When appropriate, we will aim to collect biological samples from each patient for translational research (see below) including archival tumour sample, fresh tumour biopsy or resection sample when available, blood samples at different time intervals before, during and after their treatments as well as saliva and mouth swab at the same time points when appropriate. The samples will be analysed to further assess the tumour microenvironment, the peripheral immune response and to identify predictors of treatment response.

For all patients, blood samples will be collected at baseline (at time of consent), before the first round of hyperthermia/radiotherapy treatment*, after the first round of hyperthermia/radiotherapy

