treatment**, 6 weeks (+/- 2 weeks)*** post hyperthermia/radiotherapy, 12 weeks (+/- 2 weeks)*** post hyperthermia/radiotherapy, and at the first disease progression post hyperthermia/radiotherapy. Additionally, for those patients who will subsequently undergo anti-PD1/PD-L1 checkpoint inhibitor therapy (immunotherapy) as part of the standard of care, we will collect blood samples at immunotherapy baseline, 3 weeks (+/- 2 weeks) post-immunotherapy baseline, 6 weeks (+/- 2 weeks) post-immunotherapy baseline and at the first disease progression post-immunotherapy baseline. Other samples for translational research will be collected on clinician's discretion and up to a total of six times. As a standard of care, we routinely collect patient reported outcomes to assess toxicity to radiotherapy treatment thus we will continue to collect for this study.

* May be omitted if baseline bloods have been obtained. Omission would occur due to logistical issues (i.e., difficult to arrange with the participant).

** This could usually be done after 3rd fraction of radiotherapy (if not possible, aim for 4th fraction of RT).

*** This allows for flexibility; due to the nature of the study, it may be that logistically issues make it difficult to arrange precisely at the exact timepoint.

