This is a real-world implementation study, and the patients participated in this study will undergo superficial hyperthermia in addition to SOC palliative radiotherapy. Hyperthermia treatment has not shown to significantly increase acute or late toxicities compared to radiotherapy alone. In a summary of the clinical outcomes of 38 clinical trials across various tumour sites using hyperthermia did not report any significant increase in reported acute or late toxicity with the addition of hyperthermia (19). Similarly, in a systematic review of the use of hyperthermia in addition to radiotherapy for head and neck cancer (20), did not report any worsening toxicities from the addition of hyperthermia, apart

from one study reporting a 30% increase of thermal blisters however both older radiotherapy and hyperthermia techniques have been used (22). The Hydrosun system has been evaluated in superficial breast cancer re-irradiation with no acute grade 2-4 toxicities been observed, including no burning with blistering (18). We will collect safety profile data from the patients undergoing superficial hyperthermia with SOC palliative radiotherapy in this study.

- **Procedures for Recording and Reporting Adverse Events**

No serious adverse events (SAEs) are expected to occur due to hyperthermia alone, but it can sensitize radiotherapy. For patients undergoing palliative radiotherapy and hyperthermia, they will be followed up by their treating clinicians as per normal practice.

The HRA gives the following definitions for Safety Reporting (Research other than Clinical Trials of Investigational Medical Products (CTIMPs)) for UK Health Departments' Research Ethics Service (RES):

Serious Adverse Event (SAE) is defined as an untoward occurrence that:

- a) Results in death; or
- b) Is life-threatening; or
- c) Requires hospitalization or prolongation of existing hospitalization or
- d) Results in persistent or significant disability or incapacity; or
- e) Consists of a congenital abnormality or birth defect; or
- f) Is otherwise considered medically significant by the investigator.

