In line with the study sponsor conditions and HRA guidance, if a SAE is discovered and thought to be related to superficial hyperthermia (+/- SOC palliative radiotherapy), the CI will immediately report upon knowledge of the event to the R&D Department within 24 hours. If the SAE is considered to be related to superficial hyperthermia (+/- SOC palliative radiotherapy) and unexpected, it will also be reported to the relevant REC committee within 15 days of the CI becoming aware of the event. The HRA defines SAEs as related to the study if it involves the administration of any of the research procedures and unexpected as in that it was not listed in the protocol as an expected occurrence. If the CI deems a SAE to be disease-related and not related to the superficial hyperthermia (+/- SOC palliative radiotherapy), the SAE will be documented but only reported in the final study report. Therefore, only SAEs that are localised to the site of hyperthermia (local adverse events) will be reported. Participants will be monitored for SAEs for 6 weeks after completion of radiotherapy. All documentation relating to SAEs will be kept in the Trial Master File.

12. Compliance and withdrawal

- **Subject compliance**

We will monitor the percentage of approached participants who consent to taking part in the study during the first year of recruitment.

- **Withdrawal/dropout of subjects**

We will monitor the percentage of participants who withdraw consent or drop out from the study after taking part. We will replace the subjects if necessary to make up the total target number of patients (n=30) as long as this is within the recruitment period.

- **Protocol compliance**

The patients will undergo routine treatments as per standard of care.

13. Data

- **Data management**

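### Local adverse events of any grade are the safety endpoint in Table 1, but only SAEs have a stated window after treatment, so non-serious reactions that appear after the last heat session are liable to be missed

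*Protocol*

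**What the plan says.** The protocol describes the safety endpoint in four places.

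- **Synopsis (Section 4), secondary endpoint 2:** "Local serious adverse events (SAEs) will be assessed by Common Terminology Criteria for Adverse Events (CTCAE) version 5.0".
- **Table 1 (Section 6), the same endpoint:** "Local adverse events (AEs) and adverse reactions (ARs) will be assessed by Common Terminology Criteria for Adverse Events (CTCAE) version 5.0". No time window is given.
- **Section 7, Study design:** "Patients will be assessed during their treatment for toxicities, and rate of adverse events will be assessed by CTCAE version 5.0". The sentence after it leaves follow-up to standard of care.
- **Section 11, Assessment of Safety:** "Participants will be monitored for SAEs for 6 weeks after completion of radiotherapy", and "only SAEs that are localised to the site of hyperthermia (local adverse events) will be reported".

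Table 2 lets the clinician choose among five radiotherapy schedules. The shortest is 20Gy in 5 fractions ("Daily over 1 week") and the longest is 36Gy in 6 weekly fractions. The schedule of events lists questionnaires, samples and medical record monitoring, but no adverse event or CTCAE row at any visit. Section 11 names one heat-specific toxicity from earlier work ("from one study reporting a 30% increase of thermal blisters"), notes that older techniques were used, and reports no blistering in the earlier breast re-irradiation study of this device.

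**The concern.** The endpoint in Table 1 covers events of any seriousness, while the only follow-up period with a stated end covers serious events. A local reaction that does not meet the SAE definition in Section 11 and appears after the last session has no stated time at which anyone grades it. Because the on-treatment period is set by the schedule, patients would also be observed for different lengths of time.

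Tolerability of the combination is a secondary objective, and Section 14 intends the data to inform a later study. An event that was never graded cannot be recovered by any later analysis, so this has to be fixed in data collection and cannot be left to an analysis plan.

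**Working it through.** **Inputs.** Fractions and frequency come from Table 2 and heat sessions from the text below it. The 42 days are the six-week SAE period in Section 11. I assume a Monday start, no missed sessions, and heat given on radiotherapy days within the stated week.

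**Course length, first to last fraction inclusive.**

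- Five daily fractions: 5 days.
- Ten daily fractions over two weeks: 5 + 2 + 5 = 12 days.
- Six fractions twice weekly, the two in a week 3 days apart: 1 + 2 × 7 + 3 = 18 days, approximately.
- Weekly fractions: 1 + 7 × (n − 1), so 29 days for n = 5 and 36 days for n = 6.

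These agree with the protocol's nominal one to six weeks.

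| Schedule | Course (days) | Heat sessions | Days from last heat session to last fraction | Course + 42 days |
|---|---|---|---|---|
| 20Gy/5 daily | 5 | 2 | 0 to 3 | 47 |
| 20Gy/10 daily | 12 | 4 | 0 to 3 | 54 |
| 27Gy/6 twice weekly | about 18 | 3 | 0 or 3 | about 60 |
| 20Gy/5 weekly | 29 | 5 | 0 | 71 |
| 36Gy/6 weekly | 36 | 6 | 0 | 78 |

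For the fourth column: in the weekly schedules heat precedes radiotherapy on the same day, so the last session and the last fraction coincide. In the daily schedules the second session of the final week falls on its second day at the earliest, and 5 − 2 = 3. For 27Gy/6 the last weekly session accompanies the fifth or sixth fraction.

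**Spread.** On treatment, 36/5 = 7.2 (6/1 = 6 in nominal weeks). With 42 days added, 78/47 = 1.7.

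**Time to the next scheduled visit.** The 6-week visit is allowed ±2 weeks, so it falls 28 to 56 days after the last fraction under every schedule.

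**Illustration only.** Suppose that first events occur at a constant hazard from the first fraction to 42 days after a course of d days, with a true cumulative incidence of 30% in every schedule. Then λ = −ln(0.70)/(d + 42), and on-treatment grading records 1 − exp(−λd). For d = 5, λ = 0.3567/47 and the recorded rate is 3.7%. For d = 36, λ = 0.3567/78 and it is 15.2%. The schedules between give 7.6%, 10.1% and 13.6%. The captured share runs from 12% to 51%. With a true incidence of 10% to 50%, it is 11–14% for the shortest course and 47–55% for the longest. If all reactions arose during the course, nothing would be lost. The documents give no onset times, so they do not say where between these cases the trial lies.

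**The case against.** The protocol never says that non-serious events are assessed only during treatment. The CTCAE clause in Section 7 carries no time limit of its own, medical record monitoring runs to 12 months, and patient-reported outcomes, which Section 7 describes as a measure of radiotherapy toxicity, run to 12 weeks. This stands in part: observation after treatment is not absent. But neither route is tied to CTCAE grading at the heated site, and the head and neck questionnaire goes to one cohort only.

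If the synopsis governs, the endpoint is local SAEs, the six-week window covers it for every schedule, and the concern about non-serious events falls away. That is correct, and it is why the conflict with Table 1 must be settled first.

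Three stronger readings are tempting, and the documents do not support them.

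- **That blisters and skin reactions are in fact under-counted.** There are no onset data, and reactions arising soon after a session could largely fall within the course. The one blister figure comes from older techniques, and the earlier device study reported none.
- **That comparisons between cohorts or schedules are biased.** None is planned for toxicity. The shortest and longest courses sit in the same Table 2 category of previous treatment, so no direction of bias follows. Dose and heat sessions (2 to 6) differ as well, so equal windows would not make the schedules comparable.
- **That grading stops at the third fraction.** The footnote "This could usually be done after 3rd fraction of radiotherapy" concerns blood sampling and does not limit toxicity checks. Measured from the last fraction, the interval to the next visit is the same for all schedules.

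**Conclusion.** The point holds as a gap in data collection together with an internal contradiction. Table 1 asks for local events and reactions of any seriousness. The only stated assessment period for them is the treatment course, which is 5 to 36 days long and leaves about 0 to 3 days after the last heat session. The six-week period after radiotherapy is reserved for SAEs. Late non-serious local reactions are liable to be missed, and a crude rate would rest on observation times that differ 7.2-fold. The synopsis and Section 11 restrict the endpoint or its reporting to local SAEs, against Table 1 and Section 7.

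The calendar figures assume uninterrupted courses. The conclusion assumes that sites follow the text as written and that no grading rule outside the protocol fills the gap. How many events would be lost cannot be stated.

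**What to change.** 1. Reconcile the synopsis, Table 1, Section 7 and Section 11 so that secondary endpoint 2 is local adverse events and reactions of any grade, with SAE reporting kept as a separate matter.
2. Apply the protocol's existing window, from the first session to six weeks after completing radiotherapy, to all local adverse events.
3. Add a CTCAE row to the schedule of events for treatment attendances and the 6-week visit. Because that visit may fall at 28 to 56 days, record onset dates so that each event can be placed inside or outside the 42 days, and complete an early visit from the medical record.
4. Report the worst local grade in that window, described by schedule and without a comparative claim.

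A 12-week window would also be possible, but it is a preference, and it runs past the planned start of immunotherapy at 6 ± 2 weeks, which would complicate attribution. Six weeks can overlap with an early start too, but it is the window that the protocol already uses.

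The cost is an amendment and a CRF line at visits that already take place, so standard-of-care schedules do not change. The stated event rate may be higher, and the number of gradings during treatment will still differ with the number of attendances.
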